6.1.1.2 Dose Expansion

All patients will receive continuous, daily administration of HMPL-306 at RP2D and/or MTD, beginning at C1D1.

6.1.2 PK Week

The PK week is defined as 7 days prior to C1D1 where a single dose of HMPL-306 will be administered on Day 1 of PK week (Day -7 relative to C1D1). Blood samples and ECG assessments will be collected at intervals as specified in [Appendix 1](#). These samples will be analyzed for plasma concentrations of HMPL-306, 2-HG, and other biological markers as defined by the sponsor. PK week is applicable to every cohort in the dose escalation part only. See [Appendix 1](#) for more details. PK week for a particular dose cohort will be considered optional and not mandatory if PK week data from 5 patients have been collected at the same dose.

6.1.3 Medical History and Demographic Information

Medical history data will be collected at Screening and will include significant clinical disease or symptoms, surgical history, history of malignancy (including date of diagnosis, classification, prognostic evaluation, treatment performed and outcome; tumor types and outcomes of any other previous malignancies), history of smoking, alcohol consumption, drug abuse, and other medically relevant history.

At pre-screening, only demographic information and diagnosis of disease will be collected. This demographic information will include gender, race, and in some countries, year of birth. If patients go on to participate in screening, demographic information on record will be used unless an update is warranted.

6.1.4 Prior and Concomitant Medications and Concomitant Procedures

Concomitant medications may include any prescription or over-the-counter (OTC) medications used by a patient. During the Screening Period, all medications taken by a patient within 28 days prior to HMPL-306 administration should be recorded in a case report form (CRF). At scheduled subsequent visits, any drugs taken during that period and within 30 days after end of treatment should be recorded in the CRF. Subsequent new transplantation pretreatment regimens and new antitumor treatment regimens, including HSCT, during the Safety and Efficacy Follow-up Periods will also be recorded. Prior and concomitant therapies are discussed in detail in Section [7.4.1](#) and Section [7.4.2](#).

6.1.5 Lifestyle Management

Patients enrolled in this study are advised to avoid unnecessary exposure to sunlight or any other source of ultraviolet light during their participation in this study through to 30 days after the end of treatment. Patients are encouraged to wear sunglasses and apply sunscreen products with a sun protective factor of at least 15. Safety of HMPL-306 under sunlight is not yet fully understood. Further nonclinical studies are planned to fully assess the phototoxicity effects of HMPL-306 in detail.

6.1.6 Vital Signs

Vital signs, including blood pressure, body temperature, heart rate, and respiratory rate, will be monitored as per Schedule of Events ([Table 1](#) and [Table 2](#)). Patients need to sit still for 5 minutes before blood pressure measurement. Unscheduled examinations may be performed if clinically indicated.

6.1.7 Physical Examination, Weight, and Height

Physical examination and weight measurement will be conducted as per Schedule of Events ([Table 1](#) and [Table 2](#)). Physical examination includes head, neck, ears, nose, eyes, throat, skin, mucous membranes, and gastrointestinal tract, as well as cardiovascular, renal, musculoskeletal, respiratory, and nervous systems.

Height will only be measured at screening.

6.1.8 ECOG Performance Status

ECOG PS scoring will be performed per Schedule of Events ([Table 1](#) and [Table 2](#)). ECOG PS will be carefully scored in strict accordance with criteria ([Appendix 3](#)), especially to determine eligibility for enrollment.

6.1.9 Ophthalmologic Examination

Ophthalmologic examinations, including eye appearance, slit lamp examination, best corrected visual acuity, visual field, eye movement, pupil reflex, optical coherence tomography (OCT) examination, and intraocular pressure will be performed per Schedule of Events ([Table 1](#) and [Table 2](#)). If a patient has undergone the relevant examinations 60 days before treatment (C1D1), they do not need to be repeated. After starting administration of the study drug, eye appearance and slit lamp examinations will be performed per Schedule of Events ([Table 1](#) and [Table 2](#)). Other

ophthalmic examinations are to be performed if clinically indicated. If a patient develops an ophthalmic AE related to HMPL-306, the frequency of eye examinations should be increased to once per cycle until AE is resolved or stable. If retinal pigment epithelium (RPE) detachment is noted during an OCT examination, the patient may remain on the study drug with a follow-up OCT examination 2 weeks later. If RPE detachment is still observed during re-examination, the study drug dose should be reduced and an OCT examination performed again 2 weeks later. If RPE detachment is not resolving upon re-examination, the study drug dose should be further reduced or held until the RPE detachment is shown to be resolving.

6.1.10 Laboratory Evaluations

Laboratory assessments will be performed locally. The range of normal values of all study sites will be collected prior to start of the study.

6.1.10.1 Hematology – Routine

Hematology cell counts include red blood cells, platelets, reticulocytes, white blood cells and differentials (neutrophils, lymphocytes, eosinophils, monocytes, and basophils), hemoglobin and hematocrit levels will all be performed per Schedule of Events ([Table 1](#) and [Table 2](#)). Any additional routine blood tests during the study shall be arranged by the investigator on an as-needed basis.

6.1.10.2 Hematology – Blood Transfusion History and Blood Transfusion Record

Blood transfusion history, including red blood cell and/or platelet infusion within 8 weeks prior to HMPL-306 administration, will be recorded during Screening. The type of infusion, number of infusion unit(s), and date of infusion should be recorded. The pre-infusion hemoglobin level and/or platelet count should also be recorded if obtainable (either is acceptable, both are not required).

Blood transfusion record will include red blood cell and/or platelet infusion after the start of study drug administration until end of treatment (EOT) visit. The type of infusion, number of infusion unit(s), and date of infusion should be recorded. The pre-infusion hemoglobin level and/or platelet count should also be recorded if obtainable (either is acceptable, both are not required).

6.1.10.3 Hematology – Bone Marrow Aspiration and/or Biopsy

It is necessary to perform either bone marrow aspiration or biopsy, both are not mandatory. Patients with AITL that have fluorodeoxyglucose (FDG)-avid disease and will undergo positron emission tomography-computed tomography (PET-CT) imaging for screening and efficacy evaluation are not required to have a bone marrow aspiration or biopsy.

Bone marrow aspiration and/or biopsy examinations will be performed during screening, on Day 1 of Cycles 3, 5, and 7 (every 8 weeks \pm 7 days, for the first 24 weeks), then every 3 cycles (\pm 14 days) thereafter (ie, Day 1 of Cycles 10, 13, and so on), at the EOT visit, and at every efficacy follow-up assessment for applicable patients. Additional bone marrow examinations may be performed at the investigator's discretion on as-needed basis.

Results of the analyses of the morphology examination, immunophenotyping, cytogenetics, and molecular genetic testing performed during screening will be collected in the electronic case report form (eCRF).

Please refer to [Appendix 17](#) for a description of the immunophenotyping, cytogenetics, and molecular genetic testing for AML, HR-MDS, and AITL.

6.1.10.4 Blood Chemistry

Blood chemistry will all be performed per Schedule of Events ([Table 1](#) and [Table 2](#)). This assessment should include blood urea nitrogen, creatinine, glomerular filtration rate, creatinine clearance rate; uric acid, electrolytes such as sodium, potassium, magnesium, chloride, calcium, and phosphorus, and glucose, creatine phosphokinase, and liver function tests such as total bilirubin, direct bilirubin, indirect bilirubin, ALT, AST, ALP (alkaline phosphatase), lactate dehydrogenase, total protein, and albumin.

6.1.10.5 Blood Amylase and Lipase

Tests for blood amylase and lipase will be performed as per Schedule of Events ([Table 1](#) and [Table 2](#)).

6.1.10.6 Fasting Lipid Panel

Fasting lipid panel, including total cholesterol, high-density lipoprotein, low-density lipoprotein, and triglycerides, will be performed as per Schedule of Events ([Table 1](#) and [Table 2](#)).

6.1.10.7 Coagulation Indicators

Tests for coagulation indicators, including prothrombin time (PT), activated partial thromboplastin time, and international normalized rate (INR), will be performed as per Schedule of Events ([Table 1](#) and [Table 2](#)).

6.1.10.8 HbA1C

Tests for glycated hemoglobin (HbA1C) will be performed as per Schedule of Events ([Table 1](#) and [Table 2](#)).

6.1.10.9 Pregnancy Test

Female patients of childbearing potential (including those who have undergone tubal ligation) must undergo serum pregnancy test within 7 days of study drug administration (as well as prior to HMPL-306 administration on Day 1 of PK week in dose escalation) and record a negative result. After enrollment, serum or urine pregnancy test will be performed as per Schedule of Events ([Table 1](#) and [Table 2](#)).

NOTE: Postmenopausal is defined as at least 12 months of amenorrhea without alternative medical cause.

6.1.10.10 Urinalysis

Urinalysis (or dipstick), including urine glucose, protein, ketone body, red blood cells, white blood cells (WBCs), and urobilinogen, will be performed as per Schedule of Events ([Table 1](#) and [Table 2](#)).

6.1.10.11 Virological Screening

Viral serology should be tested at screening for all patients and includes HIV, HBV (HBsAg, HBsAb, HBeAg, HBeAb, and HBcAb), cytomegalovirus (CMV) (CMV antibody), and HCV (HCV antibody). If HBsAg, HBcAb, or CMV antibody is positive, CMV DNA or HBV DNA is also required to be assayed by PCR method. If CMV DNA or HBV DNA is negative, patients may be enrolled and their CMV DNA or HBV DNA should be monitored every cycle. If HCV antibody is positive, HCV ribonucleic acid is required to undergo PCR testing.

6.1.10.12 IDH Mutational Status

Patients who have reports of positive mIDH status may directly enter Screening Period without pre-screening. Patients who have not been tested for mIDH should be tested locally (via biopsy tissue collection) to determine mIDH status before enrollment.

All patients will be required to provide samples for IDH mutational status confirmation as outlined in Section [6.1.16](#).

6.1.10.13 Tumoral Sample for Patients with AITL

Results of any analyses performed by local testing on previous tumoral samples taken for confirmation of PrD prior to screening or during screening, including immunophenotyping, cytogenetics, molecular genetic testing, and Epstein-Barr virus (EBV) status, will be collected in the eCRF.

Please refer to [Appendix 17](#) for a description of the immunophenotyping, cytogenetics, and molecular genetic testing for AITL.

6.1.11 Electrocardiogram

The 12-lead ECG indicators include PR interval, QRS interval, RR interval, QT or QTcF, and heart rate. Evaluation time points are shown in [Appendix 1](#) (dose escalation) and [Appendix 2](#) (dose expansion).

6.1.12 Echocardiogram/Multigated Acquisition Scan

To evaluate ejection fraction of patients, ECHO (preferred method) or MUGA will be performed during the Screening Period, on Day 1 of every treatment cycle for the first 3 cycles, every other cycle thereafter, and at EOT visit. It is recommended to use the same assessment method throughout the study for each patient for consistent and uniform interpretation of the results.

6.1.13 Safety Evaluation

AEs emerging as a result of protocol-required procedure(s) are collected, even during pre-screening period if applicable. AEs are collected from the signing of the ICF until 30 days after the end of treatment or initiation of new antitumor therapy. Related AEs will be followed

until they are recovered to the baseline status, already in a stable state as assessed by the investigator, start of new antitumor therapy, lost to follow-up, death, withdrawal of informed consent, end of study, or it has been confirmed the AEs are unrelated to the study drug.

Serious adverse events (SAEs) are collected from the signing of the ICF (pre-screening ICF if applicable) until 30 days after the end of treatment or initiation of new antitumor therapy, whichever is earlier. After this 30-day period, and if the patient has not started any other antitumor treatment, investigators should report only SAEs considered to be related to the study drug.

6.1.14 Efficacy Evaluation

Efficacy evaluation of AML will be performed based on 2017 European LeukemiaNet (ELN) criteria ([Appendix 8](#)). Efficacy evaluation of HR-MDS will be performed based on the International Working Group response criteria in myelodysplasia ([Appendix 12](#)). Efficacy evaluation of AITL will be performed based on Lugano Classification ([Cheson 2014](#)) for Hodgkin and Non-Hodgkin's Lymphoma ([Appendix 9](#)).

Tumor evaluations will be conducted at screening, every 8 weeks (± 7 days) during the first 24 weeks (ie, Day 1 of Cycles 3, 5, and 7), and every 12 weeks (± 14 days) thereafter (ie, Day 1 of Cycles 10, 13, and so on) through EOT, or end of Efficacy Follow-up period (if applicable). Patients who discontinue HMPL-306 treatment due to reasons other than disease progression will continue tumor assessment according to previous tumor evaluation schedule until disease progression, as defined in [Appendix 8](#) and [Appendix 9](#), or start of new antineoplastic therapy (see [Table 1](#)). The same imaging procedure and laboratory tests used to define measurable lesions at baseline should be used throughout the study for each patient.

The baseline tumor assessment should be completed within 28 days prior to the first dose of study treatment (depending on the patient's disease status, a window may be acceptable based on a discussion between the investigator and the sponsor's medical monitor). Tumor assessments completed as standard of care, prior to signing of the informed consent and within 28 days of first dose of study treatment, may be used as baseline assessment.

Response evaluation of patients will be based on the most recent results of physical, bone marrow (if applicable), imaging, and hematological examinations, per local assessment. If a patient needs to delay the study drug after bone marrow examination and wait for recovery of peripheral blood count, then routine blood test results within 2 weeks after bone marrow analysis can be used to determine response.

For patients with myeloid malignancies, this assessment should be done using a blood test, bone marrow aspiration and/or biopsy, and physical examination as per the Schedule of Events (see [Table 1](#)).

For patients with hematological malignancies that are non-myeloid (eg, AITL), all measurable and evaluable lesions should be assessed and documented at screening and each subsequent efficacy evaluation using contrast-enhanced CT scans (neck, chest, abdomen, and pelvis) for non-FDG-avid disease and/or PET-CT scans for patients with FDG-avid disease. Enhanced magnetic resonance imaging (MRI) may be used instead of CT scans in patients for whom CT scans are contraindicated.

If a patient with non-FDG-avid disease has documented bone marrow involvement at screening, a bone marrow aspirate and/or biopsy will be required at each efficacy evaluation.

6.1.14.1 Risk Stratification/Prognostic Scoring

Prognostic stratification will be collected at screening as follows:

- AML: ELN Risk stratification by genetics ([Appendix 15](#))
- HR-MDS: IPSS-R ([Appendix 16](#))
- AITL: International Prognostic Index ([Appendix 14](#))

6.1.14.2 Ann-Arbor Staging

Please refer to [Appendix 13](#) for a description of Ann-Arbor staging for patients with AITL collected at screening.

6.1.15 Pharmacokinetics and Pharmacodynamic Evaluations

6.1.15.1 Sample Collection and Handling

Blood samples will be collected for PK and PD analysis of HMPL-306 and 2-HG levels in plasma, respectively. The full PK and PD evaluation schedule of dose escalation and expansion cohorts is presented in [Appendix 1](#) and [Appendix 2](#), respectively.

The collection, handling, and transportation of biological samples should be performed in accordance with required processes as provided in study-specific laboratory manual.

6.1.15.2 Analytical Procedures

Plasma samples will be analyzed to determine concentrations of HMPL-306 using a validated, specific, and sensitive liquid chromatography-tandem mass spectrometry method. Plasma samples will be analyzed to determine concentrations of 2-HG using a validated method.

Plasma samples may also be analyzed to document the presence of circulating metabolites of HMPL-306 using a qualified research method. If conducted, metabolite analysis will be reported outside of the clinical study report (CSR).

6.1.16 IDH Mutation Confirmation

Samples will be collected for central confirmation of mIDH status in order to validate local results and reports used by sites to determine eligibility for the study. Collected samples will follow specified procedures as indicated in laboratory manual. Bone marrow and/or whole blood will be collected for analysis as described in [Appendix 1](#) (dose escalation) and [Appendix 2](#) (dose expansion). This independent confirmation will use NGS by the central laboratory at prespecified intervals as determined by the sponsor. All samples should be prepared, labeled, handled, packaged, stored, and transported in accordance with required processes as provided in study-specific laboratory manual.

6.1.17 Exploratory Biomarker Evaluation

In this study, bone marrow and/or blood samples collected will be tested and analyzed for possible biologic marker(s) as specified/identified by the sponsor. Results from these tests and analysis of its data will be used to determine correlation between possible biomarkers of HMPL-306, hematological malignancies under study, and their relationship to PK, drug exposure, TE, PD, and clinical response, as well as potential mechanism of drug resistance.

Bone marrow/blood samples collected as per [Appendix 1](#) (dose escalation) and [Appendix 2](#) (dose expansion) will be tested further for a spectrum of levels and abundance of molecular mutations and genetic aberrations (as determined by the sponsor) to evaluate their association with all tumor types under study. Results from these tests, and the analyses thereof, will be used to further characterize and fully understand biological relationship between expression levels of these molecular mutations and genetic aberrations and their correlation to PK, drug exposure, TE, PD, and clinical response of HMPL-306, as well as potential mechanisms of drug resistance.

All related analyses will be performed by the central laboratory, and all samples should be prepared, labeled, handled, packaged, stored, and transported in accordance with required processes as provided in study-specific laboratory manual.

6.1.18 End of Treatment Visit

Patients who have completed the study or have discontinued study treatment will be asked to return to the investigational site to have safety examinations and assessments within 7 days (± 3 days) after the last dose of the study drug.

6.1.19 Follow-up Period

Safety Follow-up

All patients who have completed an EOT Visit will have a Safety Follow-up Visit. The Safety Follow-up Visit will be conducted at 30 days (± 7 days) from EOT Visit.

AEs related to the study drug will be followed until resolution and SAEs will be followed until resolution regardless of the relationship to the study drug.

All female patients of childbearing potential must complete a pregnancy test (serum or urine) during the Safety Follow-up Visit. Pregnancy testing should be repeated for patients with suspected pregnancy. This is not applicable for postmenopausal female patients (defined as at least 12 months of amenorrhea without alternative medical cause), and the date of menopause should be recorded instead.

Efficacy Follow-up

Patients who discontinue the study drug due to reasons other than disease progression, death, lost to follow-up, or withdrawal of consent will remain on study for tumor assessments and will be followed every 12 weeks (± 14 days) from the EOT visit or last assessment, until disease progression, initiation of new anticancer therapy, withdrawal of consent, lost to follow-up, death, conditions are met per Section [6.2.1](#), or the end of the study, whichever comes first.

Survival Follow-up

All patients will be followed for survival status every 12 weeks (± 14 days), until death, lost to follow-up, or withdrawal of consent. Survival information can be obtained via phone and information will be documented in the source documents and relevant CRFs.

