6.2 Discontinuation or Withdrawal

6.2.1 Discontinuation of Treatment

6.2.1.1 Permanent Discontinuation of Treatment

The investigator has the right to discontinue a patient from the study for any medical condition that the investigator or sponsor determines is in the best interest of the patient; reasons may include non-compliance (eg, missed doses, visits) or pregnancy.

Any patient who discontinues treatment should be encouraged to return to the study site for an EOT Visit and continue with the remaining study visits. The primary reason(s) for discontinuation must be recorded on appropriate CRF.

Patients must be discontinued from treatment for disease progression, withdrawal of consent, intolerable toxicity, as outlined in [Table 8](#), [Table 9](#), and [Table 10](#), repeated non-compliance or poor compliance, commencement of other antitumor treatment during the study, pregnancy, loss to follow-up, termination of the study by the sponsor, death, or end of the study.

Patients may receive a maximum of 6 cycles of therapy unless the following are met:

- Patients with AML must have a partial response (PR) or better based on the 2017 ELN criteria ([Appendix 8](#)).
- Patients with HR-MDS must have a hematological response or better based on the IWG Criteria ([Appendix 12](#))
- Patients with AITL must have a stable disease (SD) or better based on the Lugano Classification ([Appendix 9](#)).

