6.2.2 Study Stopping Rules

Safety will be monitored continuously throughout the conduct of the study by a standing SRC. There will be periodic review of emerging data on safety, PK, drug exposure, TE, PD, and clinical response to determine continuation (or otherwise) of individual patient, cohorts, arms, or entire dose expansion part. If the study is halted as per Study Stopping Rules (Section 6.2.2.2) in either the dose escalation part or the dose expansion part, the study will only be restarted after Regulatory Approval as per local regulations.

Dose stopping rules for individual patients common to both dose escalation and dose expansion parts include:

1. DLTs that occur outside the DLT assessment window (DLT-equivalent) that have not resolved to Grade 1 or lower within 14 days, or after medical intervention as specified in Section 4.1.1.
2. Progression of disease that leads to treatment discontinuation
3. In the opinion and recommendation of the PI, or individual patient on their own, may withdraw from study at any time
4. If there is documented evidence of repeated non-compliance

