- Primary refractory AML unsuitable for intensive chemotherapy or venetoclax-based regimen or target agents;
- Relapsed/refractory AML that has progressed on prior IDH treatment

The sponsor, in consultation with SRC, may decide to increase or decrease the number of enrolled patients in each cohort, depending on preliminary clinical response, safety signals, or operational feasibility. Patients who are not efficacy evaluable in any cohort may be replaced.

The overall study schema is presented in [Figure 1](#).

Figure 1 Study Schema

Any patient who discontinues treatment should be encouraged to return to the study site for an End of Treatment (EOT) Visit and continue with the remaining study visits. Patients must be discontinued from treatment for disease progression, withdrawal of consent, intolerable toxicity, repeated non-compliance or poor compliance, commencement of other antitumor treatment during the study, pregnancy, loss to follow-up, termination of the study by the sponsor, death, or end of the study.

Patients who discontinue the study drug due to reasons other than disease progression, death, lost to follow-up, or withdrawal of consent will remain on study for tumor assessments and will be followed every 12 weeks (± 14 days) from the EOT visit or last assessment, until disease progression, initiation of new anticancer therapy, withdrawal of consent, lost to follow-up, death, conditions are met, or the end of the study, whichever comes first. Survival information can be obtained via phone and information will be documented in the source documents and relevant case report forms (CRFs). The end of study is defined as the date on which all patients have their last visit or 1 year after the last patient has their first visit, whichever comes first.

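### Protocol 6.1.19 ends efficacy follow-up on treatment-stop conditions that most patients in it have already met, contradicting 6.1.14; 6.2.1.1 and 6.2.2 also blur stopping drug with leaving the study

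*Protocol*

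**What the plan says.** **Efficacy follow-up.** Protocol 6.1.19 covers patients who stop drug for a reason other than progression, death, loss to follow-up or withdrawal of consent. They "will remain on study for tumor assessments" every 12 weeks until the first of several events. The list runs through progression and "initiation of new anticancer therapy, withdrawal of consent, lost to follow-up, death, conditions are met per Section" 6.2.1, and closes with the end of the study.

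**Section 6.2.1.** Its title is Discontinuation of Treatment. In 6.2.1.1, "Patients must be discontinued from treatment for disease progression, withdrawal of consent, intolerable toxicity" and for further reasons including poor compliance and pregnancy. The same subsection sets a cap: "Patients may receive a maximum of 6 cycles of therapy unless the following are met", which for AML means a PR or better. It also states: "The investigator has the right to discontinue a patient from the study for any medical condition that the investigator or sponsor determines" to be in the patient's interest, with non-compliance and pregnancy as examples.

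**Stopping rules.** Protocol 6.2.2 introduces a list of dose stopping rules for individual patients. Item 3 reads: "In the opinion and recommendation of the PI, or individual patient on their own, may withdraw from study at any time".

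**Text pointing the other way.** Under 6.1.14, patients who stop for reasons other than progression "will continue tumor assessment according to previous tumor evaluation schedule until disease progression" or new antineoplastic therapy. Section 6.2.1.1 encourages patients who stop treatment to attend the remaining visits. Section 6.2.1.2 keeps transplant patients in efficacy follow-up. Section 6.2.1.3 asks for every effort to obtain information unless consent is withdrawn. Survival follow-up in 6.1.19 covers all patients until death, loss to follow-up or withdrawal of consent.

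**SAP 2.2** repeats the list without the section number: "initiation of new anticancer therapy, withdrawal of consent, lost to follow-up, death, conditions are met, or the end of the study, whichever comes first".

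**The concern.** The cross-reference makes sense in the sentences of 4.1.1 and 4.1.2 that say how long dosing lasts. In the efficacy follow-up sentence it is circular, because a patient stopped for toxicity met a Section 6.2.1 condition before follow-up began. A site that follows 6.1.19 to the letter stops marrow assessments at the end-of-treatment visit; a site that follows 6.1.14 continues them.

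If assessments stop, later progression is not observed. If the patient then starts new therapy, SAP Table 7 rule 6 censors PFS at the last adequate assessment, although under 6.1.14 progression might have been recorded first. Patients who stop for toxicity or lack of response are unlikely to have the same outlook as those still on drug, so this censoring would be informative and would tend to make PFS and duration of response look longer.

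The wording on leaving the study raises a second question. A patient removed by the investigator for a worsening condition may drop out of survival follow-up, which 6.1.19 does not allow.

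**Working it through.** The plan states no figure for this point, so the check is mainly a reading of the texts side by side.

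**1. What the cross-reference adds.** Compare the end-events that 6.1.19 names itself with the content of 6.2.1.

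| Condition in 6.2.1 | Already named in 6.1.19? |
|---|---|
| Progression, other antitumor therapy, withdrawal of consent, loss to follow-up, death, end of study | Yes |
| Intolerable toxicity, non-compliance, pregnancy, 6-cycle cap | No; these are routes into efficacy follow-up |
| Termination by the sponsor | No; a genuine end to follow-up |
| Investigator discontinuation from the study (6.2.1.1) | No |
| Stop for transplant (6.2.1.2) | No; but expressly kept in efficacy follow-up |

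Apart from sponsor termination, the phrase adds only treatment-stop reasons and the investigator's removal power.

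**2. Assessment interval.** Section 6.1.14 keeps the previous schedule: every 8 weeks to week 24, then every 12. Section 6.1.19 says every 12 weeks from the end-of-treatment visit or last assessment. Before Day 162, SAP 4.2.3 treats a gap of 63 days or more as one missed assessment, so a 12-week gap (84 days) is flagged as a missed visit. It stays below the smallest two-visit limit (126 days), so event status is unchanged.

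**3. Effect by endpoint if assessments stop with the drug.**

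- *PFS.* Progression after the stop is missed. Stable disease at the 6-cycle cap, last assessed on C7D1 (6 × 28 + 1 = Day 169), would be censored at 169/30.4375 = 5.55 months if no death is counted. Death is still an event unless two or more assessments were missed. From Day 169 the limit is a gap of 196 days, so death counts through Day 169 + 195 = 364, absent new therapy.
- *Duration of response.* CR on Day 57, toxicity stop on Day 80 and last assessment on Day 87 would give (87 − 57 + 1)/30.4375 = 1.02 months, censored. The limit is 126 days, so death counts through Day 87 + 125 = 212. Patients capped for lack of a PR generally do not enter this endpoint.
- *EFS.* Patients without CR by week 24 are events at first dose under Table 4 rules 3 and 4 (given adequate assessments; rule 9 censors otherwise). The cap falls at 6 × 28 = 168 days = 24 weeks, so capped patients are included. Only relapse in CR responders can be missed.
- *OS.* Survival follow-up has no Section 6.2.1 exit. It is exposed only if a patient is removed from the study. Table 6 would then give the reason as alive, with censoring at the last known alive date.

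**4. Illustration with assumed hazards; none is in the documents.** Take a progression-or-death hazard λ = 0.20 per month on drug, kλ after the stop, and a stop hazard s = 0.05 or 0.10 (s/(λ + s) = 20% or 33% stop first). True PFS at t = 6 months is

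S(t) = e^(−(λ+s)t) + s·e^(−kλt)·[e^((kλ−λ−s)t) − 1]/(kλ − λ − s).

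| k | s = 0.05 | s = 0.10 |
|---|---|---|
| 2 | 0.267 | 0.240 |
| 3 | 0.251 | 0.211 |

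Censoring every patient at the stop gives e^(−1.2) = 0.301. With k = 1 there is no bias. For these hazards the gap of 0.03 to 0.09 is an upper figure, because the calculation discards all deaths after the stop and the SAP does not.

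**The case against.** The best defense is that Section 6.2.1 also holds study-exit provisions (6.2.1.3 on withdrawal, 6.2.1.5 on loss to follow-up, and sponsor termination), so the reference may mean only those; any other reading defeats the paragraph it sits in. But withdrawal and loss to follow-up are already listed separately in 6.1.19. Beyond sponsor termination, what this reading adds is mainly the investigator's power to remove a patient from the study, which is itself in conflict with survival follow-up. The ambiguity remains.

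Other objections do stand. A reader might infer that every patient entering efficacy follow-up has already met the condition. Transplant stops are expressly retained, and a patient who simply chooses to stop drug is not on the 6.2.1.1 list. A reader might also infer that outcomes after the stop are lost. Sections 6.1.14, 6.2.1.1, 6.2.1.2 and 6.2.1.3 and the follow-up columns of Tables 1 and 2 all provide for continued observation, so outcomes may be lost at some sites, not by design.

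Item 3 of 6.2.2 is introduced as a dose stopping rule, which limits it in context. The SAP 2.2 sentence is descriptive, and no censoring rule in SAP 4.2 uses it. The endpoints are secondary, no hypothesis is tested, and results are shown by small dose cohorts, with the single Part 2 patient merged into Cohort 8 (SAP Table 13), so estimates will be imprecise in any case.

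**Conclusion.** The concern holds as an internal contradiction. Section 6.1.19, read literally, ends tumor assessment when drug stops for most patients it is meant to cover, while 6.1.14 and parts of 6.2.1 require it to continue; the SAP does not settle the matter. The wording in 6.2.1.1 and 6.2.2 item 3 is a separate, smaller conflict with survival follow-up.

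At stake is progression after the stop (PFS) and relapse in responders (duration of response, and EFS for CR responders). It is tempting to conclude that PFS, EFS, duration of response and OS are all biased upward. The documents do not support that: non-CR stops by week 24 are EFS events at first dose, deaths count within the missed-visit limits, and OS depends on actual removal from the study.

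The size cannot be computed, because the documents do not say how many patients stop for these reasons, how sites read the sentence, or what the hazard is after stopping. The 0.03 to 0.09 figure rests wholly on assumed hazards and is not an estimate for this trial. The correction is worth making because it costs almost nothing.

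**What to change.** 1. In Protocol 6.1.19, delete the Section 6.2.1 condition from the efficacy follow-up sentence, or point it only to study withdrawal under 6.2.1.3. Delete the matching undefined condition from SAP 2.2. Reconcile 6.1.19 with 6.1.14 on when assessments end and at what interval.
2. In 6.2.1.1, change the investigator's right from discontinuing a patient from the study to discontinuing study treatment. Limit 6.2.2 item 3 to stopping drug. Only death, withdrawal of consent, loss to follow-up or end of study should then end survival follow-up.
3. If removal by the investigator remains possible, name it as a censoring reason in SAP Tables 6 and 8, which now have no such category.

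The cost is protocol and SAP wording; the follow-up visits and calls are already scheduled. No criterion for stopping treatment changes.
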